#### **1.2** STUDY DESIGN

Document template OTH.STAT.010 v3

This is a prospective, multicenter, open-label extension (OLE) study on the efficacy, safety, participant outcome measures, tolerability, immunogenicity, PK, and PD of EFG PH20 SC in adult PV or PF participants, who participated in the antecedent study ARGX-113-1904 (1904).

Participants at the End of Study (EoS) visit or Early Discontinuation (ED) visit in 1904 will be given the option to enroll into 1905 after confirmation of eligibility while retaining the blinding of 1904. For each participant, the date of the baseline visit in 1905 will be the same as the date of the EoS/ED visit in 1904.

At baseline, participants will be treated according to their clinical status at EoS of 1904, as follows:

SGS	Statistical Analysis Plan	
ARGX-113-1905	Final analysis	Final 1.0 of 26APR2024

- Participants who have achieved CRmin or CRoff and are not currently in flare will be observed every 4 weeks through on-site visits without EFG PH20 SC treatment. In participants who have achieved CRmin (oral prednisone ≤10 mg per day for 2 months [8 weeks]), prednisone tapering may be pursued upon investigator's judgment until participants achieve CRoff.
- Participants in CR who have not achieved CRmin will receive weekly EFG PH20 SC administrations of 1000 mg while continuing the add-on therapy of oral prednisone until CRmin is achieved. Prednisone tapering may be pursued upon investigator's judgment until participants achieve CRoff. Participants will be treated through on-site visits or through home visits with an on-site visit once every 4 weeks.
- Participants who have achieved DC but not CR will receive weekly onsite administrations of 1000 mg EFG PH20 SC with an add-on therapy of oral prednisone until CR has been achieved, and then will continue to receive weekly EFG PH20 SC administrations of 1000 mg until CRmin is achieved either on-site or through home visits with an on-site visit once every 4 weeks.
- Participants under certain conditions of treatment failure as defined below, or participants with flare after having achieved CRmin, may roll over prematurely into 1905 and will be treated with EFG PH20 SC at a dose of the second s

The following types of treatment failure are considered here:

- absence of DC with oral prednisone 1.5 mg/kg/day for a minimum of 3 weeks
- participants who roll over due to prednisone-related SAE who have not achieved DC, or
- flare between DC and achieving CRmin that is not controlled by 2 dose levels of OCS above the dose at which the flare is observed and that is at least 0.3 mg/kg/day

In the absence of DC, participants will receive prednisone at the starting dose of 1.5 mg/kg/day. In case of uncontrolled flare before CRmin, participants will receive, as starting dose, the last dose from 1904. In case of flare after CRmin, participants will receive a prednisone dose in line with the severity of the flare.

• Participants who developed a prednisone-related SAE may prematurely roll over into 1905 and may be treated with EFG PH20 SC through onsite or home visits according to the clinical statuses as described above. Concomitant prednisone will be considered to fit the clinical statuses as far as compatible with the nature and severity of the SAE, with a lower dose to no concomitant prednisone being considered otherwise.

Details on the rules for prednisone dose adjustment can be found in the clinical trial protocol (CTP).

SGS	Statistical Analysis Plan	
ARGX-113-1905	Final analysis	Final 1.0 of 26APR2024

If DC is not attained after a minimum of 3 weeks of the participant receiving oral prednisone 1.5 mg/kg qd, then the participant will be considered a treatment failure and will be withdrawn from the study.

In case of flare in the period between DC and CRmin, the prednisone dose will be increased to achieve DC again. Participants who are not controlled by a dose that is 2 dose levels above the dose at which the flare is observed and that is at least 0.3 mg/kg/day, will be managed according to clinical judgment ie, either receive a further increased prednisone dose or be withdrawn from the study. Withdrawal of participants with a flare before CRmin will be defined as treatment failure.

In case of flare after having achieved CRmin (ie, while being off treatment with EFG PH20 SC), participants will be immediately treated/re-treated with EFG PH20 SC. The first day of new EFG PH20 SC treatment will define a new baseline for assessments of outcomes (DC, CR, etc.) and prednisone escalation or tapering schedule.

In the new treatment period, participants will be administered EFG PH20 SC at a weekly dose of **Sector**, followed by weekly SC administrations of 1000 mg until CRmin. Oral prednisone will be administered at a dose chosen according to clinical judgment, with the recommendation of 0.3 mg/kg qd in the case of mild flare (PDAI activity score <15) and 0.5 mg/kg qd in the case of moderate to severe flare (PDAI activity score  $\geq$ 15). The treatment goal of a new treatment period is to first achieve DC again and therefore these participants will be treated accordingly.

A new treatment period of EFG PH20 SC can be initiated in eligible participants until week 44. In participants requiring a new treatment period of EFG PH20 SC between weeks 45 and 49, the initiation will be optional and based on clinical judgment and participant consent. A new EFG PH20 SC treatment period will not be permitted after week 49 to ensure a minimum of 4 weeks of EFG PH20 SC treatment/period.

Except for oral prednisone, no other systemic therapies (eg, immunosuppressants, IVIg, immunoadsorption, anti-CD20 biologics) will be permitted during the study.

Participants or their caregivers (a person of legal age that the participant proposes to perform the administrations) may (self-)administer EFG PH20 SC after they have successfully completed (self-)administration training (in 1904 with at least one refresher training in 1905 or during 1905).

All participants and/or their caregivers will receive a home guide for transport, storage, preparation, and administration of the IMP.

The schedule of activities is in appendix 9.3.

[figure not shown]
#### **1.3** EXPECTED SAMPLE SIZE

The maximum number of participants in 1905 will be the number of participants in 1904: up to approximately 213 participants.

## 1.4 RANDOMISATION AND BLINDING

Not applicable.

Page 15 of 84

#### **1.5** INTERIM ANALYSIS

Not applicable.

#### **1.6 SOFTWARE**

SAS version 9.4 or later (SAS Institute Inc., Cary, NC, USA) will be used for programming.

#### 1.7 VALIDATION MODEL

SGS Clinical Research (SGS CR) statistics (STAT) standard operating procedures (SOPs) and work instructions (WIs) as effective at the project start will be followed throughout the project, provided the applicable regulatory requirements are still met.

Subject-level Analysis Dataset (ADSL), Analysis of Adverse Events Dataset (ADAE) and Analysis of Laboratory Test Results Dataset (ADLB) will be validated through independent programming (model C validation). The rest of the analysis will be reviewed by an independent person (model B validation).

Final analysis

# 2. GENERAL METHODOLOGY

#### 2.1 ANALYSIS SETS

#### 2.1.1 Analysis sets

The following analysis sets will be considered in the statistical analysis:

Roll-over set (ROLL):	all participants who rolled over from study 1904
Safety analysis set (SAF):	all participants who received at least 1 dose, or part of a dose, of IMP in study 1905

A participant is considered to have rolled over to 1905 once they have provided informed consent for the study (they have signed the informed consent form [ICF] for ARGX-113-1905), defined as having a complete informed consent signature date in the database.

#### 2.1.2 As planned versus as actual analysis

Efficacy endpoints, C-GTI and GTI-SL will be analyzed according to the treatment to which participants were randomized in 1904. For other endpoints, the analysis will be conducted according to the actual treatment the participant received in both 1904 and 1905 (see section 2.4.2).

#### Table 1: Phase, period and subperiod definition

Document template OTH.STAT.010 v3

CONFIDENTIAL AND PROPRIETARY

System Version: 1.0, Status: Approved, Document ID: VV-TMF-172580

SGS	Statistical Analysis Plan	
ARGX-113-1905	Final analysis	Final 1.0 of 26APR2024

Treatment period 1 is only applicable for participants who did not achieve CRmin or CRoff in 1904

Treatment	Treatment period 1 b,c	On-treatment 1	Earliest of (date of signing the informed consent form (ICF) of study 1905 and date of roll-over), with 00:00 added as time part a .	For the participants with off- treatment 1 subperiod : last IMP administration date/time in treatment period 1. For other participants: Date of week 52/EoT/ET visit, with 23:59 added as time part.
			1	For participants who don't have a week 52/EoT/ET visit: date of last contact, with 23:59 added as time part.
		Off-treatment 1	administration date/time in treatment period 1	For the participants with a next treatment period: first IMP administration date/time in next treatment period – 1 minute.
			+ 1 minute	For other participants:
			Date of week 52/EoT/ET visit, with 23:59 added as time part.	
			For participants who don't have a week 52/EoT/ET visit: date of last contact, with 23:59 added as time part.	
	Treatment n	eriod 2 is applicab	le for participants with	flare after CRmin in the roll-over

Treatment period 2 is applicable for participants with flare after CRmin in the roll-over phase or in treatment period 1 and who re-initiate IMP administration

Treatment period 2 °	On-treatment 2	First IMP administration date/time in treatment period 2	For the participants with off- treatment 2 subperiod : last IMP administration date/time in treatment period 2.
			For other participants:
			Date of week 52/EoT/ET visit, with 23:59 added as time part.
			For participants who don't have a week 52/EoT/ET visit: date of last contact, with 23:59 added as time part.

Page 18 of 84

SGS	Statistica	al Analysis Plan		
ARGX-113-1905	F	inal analysis		Final 1.0 of 26APR2024
	Off-treatment 2	Last IMP administration date/time in treatment period 2	trea adm	the participants with a next tment period: first IMP ninistration date/time in next tment period – 1 minute.
		+ 1 minute For	For	other participants:
				e of week 52/EoT/ET visit, h 23:59 added as time part.
			wee last	participants who don't have a ek 52/EoT/ET visit: date of contact, with 23:59 added as e part.
Etc c				
Follow-up		End of treatment phase + 1 minute		e of last contact, with 23:59 ed as time part.

a In case no 1905 ICF date is available, participant data will not be considered in the analysis

b Not applicable for participants who enter 1905 on CRmin. They will start immediately in Treatment period 2 of the Treatment phase in case of flare

A new treatment period is considered for participants with a flare after achieving CRmin (ie, while being off IMP treatment). A new treatment period is not considered after temporary IMP discontinuation for an adverse event. Repeat until the last on-treatment or off-treatment subperiod.

Participants who enter 1905 on CRmin, will not have a treatment period 1 in the treatment phase, but will start immediately with treatment period 2 at first IMP intake in 1905 (ie, after the first flare in 1905). Note: treatment period 2 is defined in 1905 as the treatment period starting after the first flare within 1905. Treatment given before a first flare in 1905 is considered belonging to treatment period 1.

Adverse events (AEs) and concomitant therapies will be allocated to phases and periods as described in sections 5.1.2 and 3.3.2 respectively. All other assessments will be allocated to phases (PDAI, PD, PK, albumin and LDL-C also to periods and subperiods) based on the assessment date(time).

In case of (partially) missing date(time) fields disabling allocation, information from the visit/timepoint label and protocol schedule of activities will be used to allocate to the correct phase, period and subperiod. If this is not possible (unscheduled visits or visits on a turning point between phases, periods or subperiods), assessments will be handled as follows:

- Treatment phase vs. roll-over phase: assessments will be allocated to the treatment phase unless the available parts of the assessments start or stop date/time provide evidence for allocating to the roll-over phase.
- Treatment phase vs. follow-up phase: assessments will be allocated to the treatment phase unless the available parts of the assessments start or stop date/time provide evidence for allocating to the follow-up phase.
- On-treatment vs. off-treatment subperiod within a treatment period: assessments will be allocated to the on-treatment subperiod unless the available parts of the assessments start or stop date/time provide evidence for allocating to the off-treatment subperiod.
- Multiple treatment periods: assessments will be allocated to the first period that is possible based on the available parts of the assessments start and stop date/time.

SGS	Statistical Analysis Plan	
ARGX-113-1905	Final analysis	Final 1.0 of 26APR2024

A set of subperiods will be derived over the combined treatment and follow-up phase, to support the analysis of treatment-emergent adverse events (TEAEs) versus post-TEAEs.

Subperiod	Start	End
Treatment emergent 1	Treatment phase start date/time (see Table 1)	Date of first EFG where the next EFG is at least 61 days later + 60 days a
Post-treatment emergent 1	End date/time of previous subperiod + 1 minute	Start date/time of next subperiod - 1 minute
Treatment emergent 2	First EFG date/time following the start of previous post-treatment emergent subperiod	Date of first EFG where the next EFG is at least 61 days later + 60 days a
Post-treatment emergent 2	End date/time of previous subperiod + 1 minute	Start date/time of next subperiod - 1 minute
Etc. b		

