#### 2.2.4 Analysis visits

All assessments (except safety assessments in the roll-over phase), including unscheduled assessments, will be allocated to analysis windows. Tables, listings and figures will present the analysis windows as defined below, not the CRF visits.

Allocation of assessments will be done using their relative day in the phase (ADYP) (see section 2.2.3) according to the following table:

Phase	Analysis window	Target ADYP	Lower limit ADYP	Upper limit ADYP
Roll-Over	Baseline a	-	-	-
	Week 4	29	1 [c]	43
	Week 8	57	44	71
	Week $(8 + x^{b} * 4)$	$57 + (x^{b*28})$	$44 + (x^{b*28})$	$71 + (x^{b*28})$
	Week 52	365	352	End day of phase
Treatment	Baseline a	-	-	-
	Week 1	8	1°	11
	Week 2	15	12	18
	Week 3	22	19	25
	Week $(3+x^b)$	$22 + (x^{b*7} \text{ days})$	$19 + (x^{b*7} \text{ days})$	$25 + (x^{b*7} days)$

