#### 5.1.2 Derivation rules

Treatment-emergent adverse events (TEAE) are defined as AEs starting on or after any administration of IMP in 1905 up through 60 days after the last administration of IMP prior to the AE.

Post-treatment AEs are defined as AEs that start after the 60 days after the last IMP administration prior to the AE. AEs that start during the roll-over phase are also considered as post-treatment AEs

Based on their start date/time, AEs will be allocated to the phase in which they started. Each AE will therefore be reported in only one phase. Phases are defined in section 2.2.1. In case the AE start date/time is incomplete or missing, and the AE could consequently be allocated to more than one phase, a worst-case allocation will be done in following order:

- Treatment phase vs. roll-over phase: the AE will be allocated to the treatment phase unless the available parts of the AE start and stop date/time provide evidence for allocating to the roll-over phase.
- Treatment phase vs. follow-up phase: the AE will be allocated to the treatment phase unless the available parts of the AE start and stop date/time provide evidence for allocating to the follow-up phase.

A death case is defined as an AE with outcome 'fatal'.

An AE for which the IMP was discontinued is defined as an AE with action taken 'drug withdrawn'.

Treatment relatedness will be dichotomized as follows in tables:

- Treatment related: related, probably related, possibly related or missing
- Not treatment related: not related, unlikely related

Page 49 of 84

SGS	Statistical Analysis Plan	
ARGX-113-1905	Final analysis	Final 1.0 of 26APR2024

Adverse events of special interest will be defined using MedDRA system organ class 'Infections and infestations'.

Injection-related reactions (IRRs) will be defined as all AEs with MedDRA preferred terms that are listed in either:

- Hypersensitivity standardized MedDRA query (SMQ) (broad selection)
- Anaphylactic reaction (SMQ) (broad selection)
- Extravasation events (injections, infusions and implants) (SMQ) (broad selection), excluding implants

AND occurring within 48 hours of an administration, or within 2 days in case no AE start time is available. In case of partially missing AE start date, the AE will be considered as an IRR, unless the available parts of the AE start date provide evidence it did not occur within 48 hours of an injection.

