- TEAEs for which the IMP was discontinued
- TEAEs of special interest
- Treatment related TEAEs of special interest
- TE IRR events
- Serious TE IRR events
- TE ISR events

All AEs, including pre-treatment events will be listed.

Separate listings will be prepared for serious AEs, AEs for which IMP was discontinued, fatal AEs and AESIs. A listing showing all coding information will be prepared as well.

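### SAP Table 2 and SAP 5.1.2 start the treatment-emergent clock at different moments for participants with treatment period 1, and the SAP does not say which rule governs AEs between consent and the first 1905 dose

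*SAP*

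**What the plan says.** - **Purpose of SAP Table 2 (section 2.2.1).** Its subperiods are derived "to support the analysis of treatment-emergent adverse events (TEAEs) versus post-TEAEs". Treatment emergent 1 starts at "Treatment phase start date/time (see Table 1". Treatment emergent 2 starts at an efgartigimod administration.
- **SAP Table 1, treatment period 1.** The phase starts at "Earliest of (date of signing the informed consent form (ICF) of study 1905 and date of roll-over), with 00:00 added as time part". No dose enters the definition.
- **Participants with a roll-over phase (CRmin or CRoff entrants).** That phase ends one minute before the first 1905 dose, so their treatment phase begins at a dose. AEs starting in the roll-over phase are classed as post-TEAEs.
- **SAP 5.1.2.** TEAEs "are defined as AEs starting on or after any administration of IMP in 1905 up through 60 days after the last administration of IMP" preceding the event. Post-treatment AEs start later than that, or in the roll-over phase.
- **SAP 5.1.2, rates.** TEAE person-years (PYFU) sum the durations in which an AE counts as treatment-emergent.
- **SAP 5.1.3.** "All AEs, including pre-treatment events will be listed".
- **SAP 2.2.2 and 2.2.4.** Visit windows use ADYP or AWADY, whose day 1 is the first day of the phase or subperiod.
- **Protocol.** TEAE incidence and severity is a primary endpoint (Section 3). AEs are collected from ICF signature (Section 8.4.1). Consent is scheduled at V1, and V1 assessments precede dosing (Section 1.3).

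**The concern.** For a participant with treatment period 1, the interval from consent to first 1905 dose lies inside Treatment emergent 1 but outside the section 5.1.2 definition. Two programmers could follow the SAP faithfully and produce different TEAE tables for the primary endpoint.

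Under 5.1.2, such an event is neither TEAE nor post-TEAE. It still falls in the overall AE count, because 5.1.3 defines that count as all AEs in the treatment and follow-up phases. For a participant with a roll-over phase, an AE in the same position is a post-TEAE. So an AE before the first 1905 dose has three possible classifications, depending on the rule and the entry route.

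The interval is not empty by design. V1 examinations, vital signs, ECG and laboratory samples all precede the injection, and clinically significant new or worsened findings are reported as AEs (protocol Sections 8.3.1, 8.3.3, 8.3.4 and 8.3.6). Such a finding arose before any 1905 dose.

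**Working it through.** The plan gives no figure to reproduce. The check applies both rules to the same cases and then sizes the side effects.

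**1. Classification (treatment period 1).** Assume a first dose at 10:00 on the roll-over day.

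| AE onset, after ICF signature | SAP Table 2 | SAP 5.1.2 |
|---|---|---|
| Same day, before 10:00 | TEAE | neither TEAE nor post-TEAE |
| 1 or 5 days before dose (consent 7 days early) | TEAE | neither TEAE nor post-TEAE |
| 1 hour after dose | TEAE | TEAE |

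The rules disagree only between signature and first dose. An AE at 07:00 on the dose day is in dispute only if consent had been signed by then.

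**2. TEAE person-time.** Extra person-years = n × lag / 365.25. Inputs: n = 213, the maximum in SAP 1.3, which also includes unaffected CRmin/CRoff entrants. The emergent window is assumed to be 52 × 7 + 60 = 424 days. Base = 213 × 424 / 365.25 = 247.3 person-years. The relative increase is lag / 424, whatever n is.

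| Assumed lag, consent to dose | Extra person-years | Increase |
|---|---|---|
| 1 day | 0.58 | 0.24% |
| 7 days | 4.08 | 1.65% |
| 14 days | 8.16 | 3.30% |
| 28 days | 16.33 | 6.60% |

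With same-day consent and a 10:00 dose, the excess from the 00:00 start is (10/24) / 424 = 0.1%. For a participant with one dose (1 + 60 = 61 days), a 1-day lag adds 1/61 = 1.64% and a 7-day lag 7/61 = 11.48%.

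**3. Visit windows, only if the ICF precedes roll-over by k days.** A visit 7 days after V1 has ADYP = 7 + k + 1 = 8 + k. SAP Table 3 gives Week 1 as days 1–11, Week 2 as 12–18 and Week 3 as 19–25.

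- k = 3: ADYP 11, Week 1
- k = 4: ADYP 12, Week 2
- k = 11: ADYP 19, Week 3

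A visit 2 days late, still inside the protocol window, has ADYP 10 + k and leaves Week 1 at k = 2. In SAP Table 5 the pre-dose V1 sample has AWADY k + 1, so for k = 1 to 10 it falls in Week 1. SAP 2.2.3 would make it the treatment-period baseline.

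**The case against.** The strongest reply is that section 5.1.2 plainly governs. It is the only express definition of a TEAE, section 2.2.1 sends AE allocation there, and Table 2 is only described as supporting the analysis. The AE onset-day formula is anchored on first IMP (though its label names the roll-over visit), and pre-treatment events are expected in the listings. This makes 5.1.2 the likelier intention. A reader might infer that pre-dose AEs will certainly be counted as TEAEs; the documents do not support that. But precedence is never stated, 5.1.2 refers back to 2.2.1 for phases, and Table 2 is the only explicit set of durations for TEAE PYFU. Using 5.1.2 for the numerator and Table 2 for the denominator would leave them mismatched.

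The reply is also right on size. Consent is scheduled at V1 with a ±0-day window, the analysis is descriptive, and CRmin/CRoff entrants with a roll-over phase are unaffected. Other inferences go too far:

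- **Every AE from midnight is affected.** Collection starts at ICF signature, so on a same-day schedule only the part of the visit between signature and injection matters.
- **Every V1 abnormality becomes a TEAE.** Only clinically significant new or worsened findings are AEs. Treatment-emergent laboratory and ECG abnormalities are judged against the V1 baseline and do not change.
- **Events are counted in both trials.** That depends on the 1904 AE rules, which are not in these documents.
- **All visit windows are displaced.** This needs consent before the roll-over visit. The choice of the earlier date in SAP Table 1 provides for that, but no lag is given. Baseline, ADY and the GTI windows stay tied to roll-over.

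**Conclusion.** The inconsistency is real and confined to participants with treatment period 1. AEs between consent and first 1905 dose have two incompatible classifications, and TEAE PYFU can include pre-dose time. It reaches a primary endpoint, so it should be resolved in the SAP.

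The numerical effect is probably small. It covers part of one visit on the documented schedule and grows only with early consent or a delayed first dose. The percentages above rest on assumed lags and on the assumed 424-day or 61-day window. The number of AEs in the gap cannot be estimated from the documents, and the net direction of the effect on event rates is unknown because numerator and denominator can both rise. The visit-window shift is conditional on early consent.

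**What to change.** - **SAP Table 2.** Start Treatment emergent 1 at the first 1905 efgartigimod date/time, as is already done for Treatment emergent 2.
- **Pre-treatment category.** Add one running from ICF to one minute before the first dose, with a matching phase or subperiod in SAP Table 1, so that every AE still has a phase. Merely moving the phase start to the roll-over date would leave AEs after an earlier consent in no phase. Keep this category out of the TEAE numerator and TEAE PYFU, and say whether it belongs to the overall AE count. If it is a separate phase, check the overall AE definition, overall PYFU and the prednisone start-date imputation, which rely on the named phases or the first phase start.
- **Day-1 AEs with no start time.** Count them as TEAEs unless the available data show pre-dose onset.
- **SAP 2.2.2.** For treatment period 1, anchor ADYP and AWADY on the roll-over visit date.

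The cost is SAP wording and a few date derivations, with no new data. The downside is that TEAE counts and person-time may fall slightly.
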